7.3 Lost to follow up

A participant will be considered lost to follow up if he or she repeatedly fails to return for scheduled visits and is unable to be contacted by the study site.

The following actions must be taken if a participant fails to return to the clinic for a required study visit:

- The site must attempt to contact the participant and reschedule the missed visit as soon as possible, counsel the participant on the importance of maintaining the assigned visit schedule, and ascertain whether or not the participant wishes to and/or should continue in the study.
- Before a participant is deemed lost to follow up, the investigator or designee must make every effort to regain contact with the participant (at least 1 phone call and 1 written message to the participant), and document his/her effort (date and summary of the phone call and copy of the written message in the source documents), to complete the final evaluation. All results of these evaluations and observations, together with a narrative description of the reason(s) for removing the participant, must be recorded in the source documents. The ClinBase must document the primary reason for withdrawal.
- Should the participant continue to be unreachable, he/she will be considered to have withdrawn from the study with a primary reason of lost to follow up documented in the ClinBase.

8 STUDY ASSESSMENTS AND PROCEDURES

Study procedures and their timing are summarized in the Schedule of Activities (Section 1.3).

Protocol waivers or exemptions are not allowed.

Adherence to the study design requirements, including those specified in the Schedule of Activities (Section 1.3), is essential and required for study conduct.

All screening evaluations must be completed and reviewed to confirm that potential participants meet all eligibility criteria. The investigator will maintain a screening log to record details of all participants screened and to confirm eligibility or record reasons for screening failure, as applicable.

In the event of a significant study-continuity issue (eg, caused by a pandemic), alternate strategies for participant visits, assessments, medication distribution, and monitoring may be implemented by the sponsor or the investigator, as per local health authority/ethics requirements.

The maximum amount of blood collected from each participant over the duration of the study, including any extra assessments that may be required, will not exceed 500mL. Repeat or unscheduled samples may be taken for safety reasons or for technical issues with the samples.

8.1 Administrative and general/baseline procedures

Participant's informed consent (see Section 10.1.3) and general medical/procedure history will be obtained at the Screening Visit. Baseline procedures including urine cotinine test, drug screen, urine alcohol test, and verification of inclusion/exclusion criteria will be performed at the Screening Visit and on Day -1. Prior and concomitant medication will be reviewed at all visits throughout the study.

8.2 Efficacy assessments

Not applicable.

8.3 Safety assessments

Planned time points for all safety assessments are provided in the Schedule of Activities (Section 1.3).

8.3.1 Physical examination

Physical examinations will be performed at the scheduled time points presented in Section 1.3.

A complete physical examination will include, at a minimum, general appearance; ears, nose, and throat; eyes, hair, and skin; and assessments of the cardiovascular, respiratory, gastrointestinal neurological (including sensation, muscle strength, reflexes, balance and mental state), musculoskeletal, and hepatic systems.

Height and weight will be measured and recorded at the Screening Visit, and the study participant's BMI will be calculated. Height will be measured with the study participant not wearing shoes, and the outcome will be rounded to the nearest 1cm. Body weight will be measured with the study participant wearing light clothing and without wearing shoes; the outcome will be rounded to the nearest 0.1kg. The BMI will be calculated (weight [kg]/[height (m²)]) and will be reported to 1 decimal place.

A symptom-directed physical examination will be performed in case of emerging symptoms. A physical examination of the skin will include, at a minimum, a visual check of the skin, and may be conducted by a nurse or physician.

Investigators should pay special attention to clinical signs related to previous serious illnesses.

Clinically significant findings or worsening of previous findings will be recorded as AEs.

8.3.2 Vital signs

Vital signs, including heart rate, systolic blood pressure (SBP), diastolic blood pressure (DBP), respiratory rate, and aural temperature will be measured after 5 minutes of rest in a supine position (in a quiet setting without distractions such as a television or cell phones). Heart rate, SBP, and DBP will be measured with a completely automated device. Manual techniques will be used only if an automated device is not available. Any clinically significant abnormality in the view of the investigator will be recorded as an AE.

Vital signs (to be taken before blood collection for laboratory tests) will consist of 3 heart rate and 3 blood pressure (BP) measurements (3 consecutive BP readings will be recorded at intervals of at least 1 minute). The average of the 3 BP readings will be recorded in ClinBase.

8.3.3 Electrocardiograms

A single 12-lead ECG will be obtained as outlined in the Schedule of Activities (Section 1.3) - but can be repeated in triplicate if clinically indicated - using an ECG machine that automatically calculates the heart rate and measures PR, QRS, QT, and QTcF intervals. Refer to Section 7.1.2 for QTcF withdrawal criteria and any additional QTc readings that may be necessary.

The study participant should be resting in the supine position for at least 10 minutes before the start of the recordings.

The investigator should review all ECG recordings and, if there are abnormalities that are considered clinically significant for a particular study participant, then the investigator should initiate a review by a specialist of all ECG data pertaining to that study participant. The following ECG parameters will be recorded in the ClinBase: heart rate, PR-interval, QRS-duration, QT-interval, QTcF, and investigator's conclusion on ECG profile.

8.3.4 Clinical safety laboratory tests

See Appendix 2 (Section 10.2) for the list of clinical laboratory tests to be performed and refer to the Schedule of Activities (Section 1.3) for the timing and frequency.

The investigator must review the laboratory report, document this review, and record any clinically significant changes occurring during the study as an AE. The laboratory results must be filed with the source documents.

All laboratory tests with values considered clinically significantly abnormal during participation in the study or within 7 days after SFU/ETV should be repeated until the values return to normal or Baseline (Day -1, or Day 1 before first treatment) or are no longer considered clinically significant by the investigator or UCB Study Physician.

If clinically significant values do not return to normal/Baseline within a period of time judged reasonable by the investigator, the etiology should be identified, and the sponsor notified.

All protocol-required laboratory tests, as defined in Appendix 2, must be conducted in accordance with the laboratory manual and the Schedule of Activities (Section 1.3).

If laboratory values from nonprotocol specified laboratory tests performed at the institution's local laboratory require a change in participant management or are considered clinically

significant by the investigator (eg, SAE or AE or dose modification), then the results must be recorded.

8.3.5 Pregnancy testing

Refer to Appendix 4 (Section 10.4) for pregnancy testing guidelines.

8.4 AEs, SAEs, and other safety reporting

The definitions of AEs and SAEs can be found in Appendix 3 (Section 10.3).

The investigator and any designees are responsible for detecting, documenting, and recording events that meet the definition of an AE or SAE and remain responsible for following up AEs that are serious, considered related to the study intervention, or that caused the study participant to discontinue minzasolmin (see Section 10.3). This includes events reported by the participant.

The method of recording, evaluating, and assessing causality of AEs and SAEs and the procedures for completing and transmitting SAE reports are provided in Appendix 3 (Section 10.3).

8.4.1 Time period and frequency for collecting AE and SAE information

All AEs and SAEs will be collected from the signing of the ICF until the SFU or ETV (if applicable) at the time points specified in the Schedule of Activities (Section 1.3) and must be reported in the ClinBase even if no study intervention was taken but specific study procedures were conducted. This includes all AEs not present before the initial visit and all AEs that recurred or worsened after the initial visit.

All SAEs will be recorded and reported to the UCB Study Physician or designee immediately and under no circumstance should this exceed 24 hours, as indicated in Appendix 3 (Section 10.3). The investigator will submit any updated SAE data to the sponsor within 24 hours of it being available.

Investigators are not obligated to actively seek information on AEs or SAEs after conclusion of the study participation. However, if the investigator learns of any SAE, including a death, at any time after a participant has been discharged from the study, and the investigator considers the event to be reasonably related to the study intervention or study participation, the investigator must promptly notify the sponsor.

The method of recording, evaluating, and assessing causality of AE and SAE and the procedures for completing and transmitting SAE reports are provided in Appendix 3 (Section 10.3).

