^b Study participants will have SFU procedures performed within 5 to 9 days after final dose. Participants who prematurely withdraw from the study will return to the clinic center for the ETV as soon as possible after the time of withdrawal and will have all SFU procedures performed.

^c Clinical assessments performed on Days 1, 6, and 11 need to be performed predose.

^d Complete physical examinations will be performed during Screening, at Day -1, and at SFU/ETV. Symptom-directed physical examinations will be performed during Treatment Periods.

^e Blood hematology and chemistry laboratory tests will be obtained in the fasting state following an overnight fast of at least 10 hours. Hepatic function tests only will also be performed 24 hours before each dosing (ie, Day 5 and Day 10). Note that FSH and estradiol will only be determined for females at the Screening Visit.

^f 12-lead ECG will be performed in single after a rest in supine position for at least 10 minutes before recordings, but can be repeated in triplicate if clinically indicated.

^g SBP, DBP, respiration rate, PR, and body temperature. Vital signs will be performed after a rest of at least 5 minutes.

^h The PK sampling timepoints will be: predose and at 0.5, 1, 1.5, 2, 4, 8, 12, 24, 36, 48, 72, and 96h after minzasolmin administration on Day 1, Day 6, and Day 11.

ⁱ Study participants will receive standard meals and snacks at appropriate times indicated by the clinic center, except when they are required to fast. All participants fast overnight for at least 10 hours before minzasolmin administration. Participants in Treatment A and B continue fasting for at least 4 hours after minzasolmin administration. Thereafter they receive a standard lunch. Fed study participants (Treatment C) should start the recommended high-fat high-calorie meal 30 minutes before administration of minzasolmin. Study participants should eat this meal in 30 minutes or less; however, minzasolmin should be administered 30 minutes after start of the meal. No food should be allowed for at least 4 hours postdose. During the rest of the day, study participants receive standard meals and snacks at appropriate times indicated by the clinic center.

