4 STUDY DESIGN

4.1 Overall design

UP0152 is an open-label, randomized, 3-treatment, 6-sequence, 3-period crossover study in healthy male and female participants designed to evaluate relative bioavailability under fasting condition of a new tablet formulation when compared with the current granules in capsule formulation used in clinical studies (Treatment B and A, respectively). The study is also designed to evaluate effect of high fat meal on the PK of minzasolmin following administration of a single dose of the new tablet formulation in fed condition (Treatment C). Eighteen participants will be randomized in the study to ensure a minimum of 2 completers in each of the 6 sequences. The study consists of a Screening Period of up to 28 days, a baseline health status assessment (on Day -1) and 3 Treatment Periods with washout periods between the treatments. After all the scheduled procedures have been performed, the participant may leave the clinic provided that, in the opinion of the investigator, there are no safety concerns. Participants will return to the clinic to complete the SFU Visit assessments 7 days (± 2 days) after the final dose (Table 4-1).

Table 4-1: Relative bioavailability of minzasolmin under fasting and fed condition (3-treatment, 6-sequence, 3-period crossover design)

Sequence	Period 1	Washout	Period 2	Washout	Period 3	Washout	Discharge	SFU
Day	D1	D2-5	D6	D7-10	D11	D12-15	D15	D18 (± 2 days)
1 (ABC)	A		B		C			
2 (BCA)	B		C		A			
3 (CAB)	C		A		B			
4 (ACB)	A		C		B			
5 (BAC)	B		A		C			
6 (CBA)	C		B		A			

D=day; SFU=Safety Follow-Up

Note: A: Granules in capsule (fasting); B: Tablet formulation (fasting); C: Tablet formulation (fed).

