8.4.5 Pregnancy

Details of all pregnancies in female study participants and, if consented, in female partners of male study participants will be collected after the start of study intervention and, until at least 12 months after the delivery date.

If a pregnancy is reported, the investigator will record pregnancy information on the appropriate form and submit it to the sponsor within 24 hours of learning of the pregnancy, and should follow the procedures outlined in Appendix 4 (Section 10.4).

While pregnancy itself is not considered to be an AE, any pregnancy will need to be reported. In some circumstances, a pregnancy report is considered as an SAE: miscarriage, elective abortion when medically indicated (eg, when pregnancy is endangering life or health of woman or when fetus will be born with severe abnormalities), unintended pregnancy after hormonal contraceptive failure (if the hormonal contraceptive was correctly used), ectopic pregnancy, fetal demise, or any congenital anomaly/birth defect of the baby.

The participant/pregnant female partner will be followed to determine the outcome of the pregnancy. The investigator will collect follow-up information on the participant/pregnant female partner and the neonate, and the information will be forwarded to the sponsor.

Any poststudy pregnancy-related SAE in either the mother or the neonate considered reasonably related to the study intervention by the investigator will be reported to the sponsor as described in Section 8.4.4. While the investigator is not obligated to actively seek this information in

former study participants/pregnant female partner, he or she may learn of an SAE through spontaneous reporting.

Any female participant who becomes pregnant while participating in the study will discontinue study intervention and return for an ETV as described in the Schedule of Activities (Section 1.3).

If the study participant decides to completely withdraw from the study, an SFU visit should be scheduled 5 to 9 days after the final dose of study intervention.

The investigator must inform the participant of any known potential risks the study intervention may have to the mother and/or the developing fetus/infant as well as any available treatment alternatives.

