5.1.1.5 Mapping of assessments performed at Early Termination Visit

Safety assessments made at an early termination visit that correspond to a scheduled visit will be summarized at the scheduled visit to correspond to the early termination visit if the assessment was scheduled to occur at that visit. Such assessments at the early termination visit will also be considered for safety follow up/ termination visit.

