5.5.2 Adverse Events

An Adverse Event is any untoward medical occurrence in a participant or clinical study participant, temporally associated with the use of study medication, whether considered related to the study medication.

Adverse events with start date/time prior to first treatment are defined as pre-treatment. These events will not be included in any tabulated summaries but will be listed.

Treatment emergent AEs (TEAE) are all AEs starting on or after the date/time of first treatment and up to including 4 days after last treatment, or any unresolved event already present before administration of treatment that worsens in intensity following exposure to the treatment.

AEs with a start date after 4 days of last treatment are defined as post-treatment. These events will not be included in any tabulated summaries but will be listed.

In case of missing or partially missing AE dates, the following rules will apply. Start and stop dates of AEs will be displayed as reported in the participant data listings (ie, no imputed values will be displayed in data listings).

The following rules will be applied for partial start dates and time:

- If only the month and year are specified and the month and year of the first treatment is not the same as the month and year of the start date, then use the 1st of the month, or the date of Screening if this is later (if the imputation results in an end date that is earlier than the start date, then use the 1st of the month). If time is missing, it will be imputed as 00:00 h
- If only the month and year are specified and the month and year of the first treatment is the same as the month and year of the start date, then use the date of the first treatment. If the imputed start date that is after the specified end date, then use the 1st of the month, or the date of Screening if this is later (if the imputation results in an end date that is earlier than the start date, then use the 1st of the month). If the imputed date is the date of treatment then time will be imputed as the start time of the treatment (ie, event will be regarded as treatment emergent)
- If only the year is specified, and the year of the first treatment is not the same as the year of the start date, then January 01 will be used. If time is missing, it will be imputed as 00:00 h

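### AE collection for a withdrawn participant can stop before the SAP's 4-day treatment-emergent window closes, and early ETV values can be summarised as follow-up values

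*Protocol*

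**What the plan says.** **End of AE collection.** Protocol 8.4.1: "All AEs and SAEs will be collected from the signing of the ICF until the SFU or ETV (if applicable". The same section says that after participation has ended the investigator need not go looking for AEs or SAEs, and must notify only an SAE that comes to light and is judged related.

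**Timing of the last visit.** For participants who finish, Schedule of Activities footnote b: "Study participants will have SFU procedures performed within 5 to 9 days after final dose". Protocol 4.1 gives the same window as 7 ± 2 days. For those who stop early, footnote b: "Participants who prematurely withdraw from the study will return to the clinic center for the ETV as soon as possible after the time of withdrawal", with all SFU procedures done there. Protocol 7.2 places the ETV at the time of discontinuation, if possible. No text sets a minimum interval between the last dose and the ETV.

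**Endpoint window.** SAP 5.5.2 counts an AE as treatment-emergent from first treatment and "up to including 4 days after last treatment". Later events are listed but not tabulated.

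**Use of ETV values.** The SAP section on mapping of ETV assessments (numbered 5.1.1.5) sends a safety value to a scheduled visit where one corresponds, and adds: "Such assessments at the early termination visit will also be considered for safety follow up/ termination visit".

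**One different rule.** Protocol 8.4.5 (Pregnancy) says that on complete withdrawal "an SFU visit should be scheduled 5 to 9 days after the final dose of study intervention".

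**The concern.** The collection period and the endpoint window are anchored to different events. The SAP's window runs from the last dose. For a withdrawn participant, collection runs to a visit timed from withdrawal. Participants stay in the clinic throughout the treatment periods, so an ETV soon after a dose is plausible. Nobody is then required to ask about new AEs for the rest of the window.

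The analysis does not show the shortfall. A dosed participant remains in the Safety Set, and SAP 5.1 bases percentages on the number in the analysis set. Days without questioning therefore count the same as days without events. Two of the three secondary endpoints are exposed: occurrence of TEAEs and occurrence of treatment-emergent SAEs. Hypersensitivity, which Protocol 2.3 names as an important identified risk, is an example of an event one would not want to leave to chance reporting.

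The mapping rule is a second, smaller matter. It can mix laboratory, vital-sign and ECG values taken shortly after a dose with values taken 5 to 9 days after it.

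**Working it through.** Days after dose are counted with the dosing day as 0.

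**1. The plan's own visit figures.** The last planned dose is on Day 11. The SFU window is Day 11 + 5 to Day 11 + 9, that is Days 16 to 20, which equals D18 ± 2. Screening plus treatment and follow-up is 28 + 20 = 48 days, the stated maximum. SAP Table 4 gives the SFU as Relative Day +6 to +10; since it numbers the dosing day 1, this is again 5 to 9 days after the dose. These figures agree.

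**2. Participants who finish.** The TEAE window ends at last dose + 4 = Day 15. The SFU is on Day 16 at the earliest, so the window is fully covered.

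**3. Participants who withdraw.** After a last dose on Day 1, 6 or 11 the window ends on Day 5, 10 or 15. With the ETV k days after the last dose:

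uncollected days = max(0, 4 − k)

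The documents do not give k, so it is an assumption, shown over its relevant range:

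| k (days from last dose to ETV) | Uncollected days | Share of the 4-day window |
|---|---|---|
| 0 | 4 | 100% |
| 1 | 3 | 75% |
| 2 | 2 | 50% |
| 3 | 1 | 25% |
| 4 or more | 0 | 0% |

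**4. Weight of one participant.** At most 18 participants receive each treatment. One missed participant with an event changes an incidence by 1/18 = 5.6 percentage points in that treatment column.

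**5. With a contact 5 to 9 days after the last dose.** The contact falls on Days 6–10, 11–15 or 16–20, always after the window has closed (Day 5, 10 or 15). Uncollected time becomes 0 days for everyone reached.

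**6. The mapping rule.** Two examples show two distinct effects.

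- *Wrong time since dose.* Dose on Day 11, withdrawal and ETV on Day 12. The laboratory value is 1 day postdose but is summarised in the SFU row, which SAP Table 4 defines as 5 to 9 days after the dose. SAP 5.1.1.7 points the same way, since it assigns early-withdrawal measurements to the end-of-study visit without regard to timing.
- *Two rows.* Dose on Day 6, ETV on Day 10. Hepatic tests are scheduled on Day 10, so the value matches that visit and is also considered for the SFU, although it is only 4 days postdose.

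A Day 12 laboratory value has no scheduled counterpart, so it need not appear twice. Duplication arises only where the ETV matches a scheduled assessment.

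**The case against.** The protocol does much to keep hold of participants who stop for a safety reason. Reported AEs are followed to resolution or stabilisation (8.4.3). Clinically significant laboratory abnormalities are repeated, including those within 7 days after the SFU or ETV (8.3.4). A participant with a possible reaction is told to contact the site at any hour (8.4.6.1). Participants with potential drug-induced liver injury are not to be withdrawn until investigation is complete (10.6). Related SAEs learned of later must be notified. The wording that withdrawn participants return to the clinic suggests a separate visit, so a same-day ETV is a worst case. Dropouts are assumed minimal.

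All of this stands as a limit on size. None of it asks a withdrawn participant with no known problem about new events up to day 4. That is the gap.

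A reader might infer more than the documents support:

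- *That TEAEs leading to withdrawal are undercounted.* Such an event precedes the withdrawal and therefore the ETV, so it is collected.
- *That being observed for less than the 5-to-9-day SFU interval biases the endpoints.* Events starting after day 4 are not tabulated, so only an ETV before day 4 matters.
- *That delayed transaminase rises would be missed.* Protocol 2.3 reports that most elevations appeared 2 to 3 months into daily dosing. A contact some days after a single dose does not address that, and a telephone call cannot detect a rise.
- *That 8.4.5 proves a general contradiction.* It is a provision for pregnancy. It does differ from footnote b and needs reconciling, and it shows that a visit in that window after withdrawal is already contemplated.

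The mapping rule touches only exploratory, descriptive summaries, and by-participant listings are planned as well. It bears on no TEAE endpoint.

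**Conclusion.** The mismatch is real and minor. Active collection of new-onset AEs can end up to 4 days before the SAP's treatment-emergent window does, for any participant whose ETV is held less than 4 days after a dose. The possible direction of error is understatement of TEAE and treatment-emergent SAE occurrence.

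The size rests on two unknowns: how many participants withdraw, and how soon the ETV follows the last dose. The documents give neither; 4 of 4 days is the limiting case, not an expectation. If nobody withdraws, or every ETV falls 4 or more days after the last dose, nothing is lost. The mapping rule is a separate tidiness point in the descriptive safety tables.

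**What to change.** **Protocol 8.4.1 and Schedule of Activities footnote b.** Keep the ETV and its procedures as soon as possible after withdrawal. Add that AEs and SAEs are collected for every dosed participant until at least the end of the 4-day TEAE window, by a contact in the existing 5-to-9-day window if the participant agrees. Ask about events since the ETV and record onset dates, so that the SAP's window can be applied. Reconcile the wording with 8.4.5, so that it is clear what follows an ETV for each kind of withdrawal.

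**SAP section on mapping of ETV assessments.** Count an ETV value in the SFU row only if it was taken 5 to 9 days after the last dose. Otherwise show it as ETV. Never enter one value in two rows. Bring the early-withdrawal rule in SAP 5.1.1.7 into line.

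**Cost.** One contact per withdrawn participant, a short protocol amendment and a few lines of SAP text. Some participants will decline the contact, and for them the gap remains.
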